### *Safety Analyses*

Safety data collection will commence when each individual subject signs and dates the informed consent form and continue until the study ends or the subject withdraws from the study, whichever occurs first. All SAEs will be reported to and reviewed by the Study Investigator. One non-study physician from the IHTC will review all SAEs, deaths or other unexpected events and report to the Study Investigator with recommendations. If a patient dies on study, the case will be evaluated in detail to determine its relatedness to the study drug and to determine if the study warrants stopping in the Study Investigator's opinion. Any death or drug-related SAE will be reported through Genentech's reporting system, as will all other required reportable events (see **Section 6.11.3.2j**). The study site will maintain a record of all SAE reports, interpretations and recommendations which will be available for Genentech to review upon request. In addition, if a greater than expected number of breakthrough bleeding events, or the development of thrombosis, thrombotic microangiopathy (TMA) or anaphylactic reaction to study medication occurs, the treatment of that patient will be halted. The Study Investigator may withdraw a patient based upon their clinical discretion and patient safety.

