#### *6.11.3.2i AEs of special interest (AESIs)*

AESIs are a subset of Events to Monitor (EtMs) of scientific and medical concern specific to the product, for which ongoing monitoring and rapid communication by the Study Investigator to the Sponsor is required. Such an event might require further investigation in order to characterize and understand it. Depending on the nature of the event, rapid communication by the trial Sponsor to other parties (eg, Regulatory Authorities) may also be warranted.

The Hemlibra (emicizumab) Events of Special Interest are:

- Thrombotic Microangiopathy
- Thromboembolic Events
- Systemic hypersensitivity reactions and anaphylactic and anaphylactoid reactions

Adverse events of special interest for this study include the following:

- Cases of potential drug-induced liver injury that include an elevated ALT or AST in combination with either an elevated bilirubin or clinical jaundice, as defined by Hy's law:
  - Treatment-emergent ALT or AST  $> 3 \times$  ULN in combination with total bilirubin  $> 2 \times$  ULN

- Treatment-emergent ALT or AST  $> 3 \times$  ULN in combination with clinical jaundice
- Suspected transmission of an infectious agent by the study drug, as defined below:
  - Any organism, virus, or infectious particle (eg, prion protein transmitting transmissible spongiform encephalopathy), pathogenic or non-pathogenic, is considered an infectious agent. A transmission of an infectious agent may be suspected from clinical symptoms or laboratory findings that indicate an infection in a patient exposed to a medicinal product. This term applies only when a contamination of the study drug is suspected

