## **7.6 End of Study/Early Termination Procedures**

The subject has the right to withdraw consent and exclude him/herself from the study at any time. The Study Investigator has the right to involuntarily withdraw a subject from the study at any time for any reason (eg, lack of compliance, unwillingness to complete study visits, SAEs, etc). The study may also be terminated early by Genentech as detailed in **Section 10.11**.

If the study is not terminated early, then the study will end 4 years following the date on the informed consent form of the first subject.

At subject withdrawal or study end/termination:

- All unused vials of Hemlibra (emicizumab) will be returned to the IHTC
- All empty vials of Hemlibra (emicizumab) will be returned to the IHTC
- The patient diary, study medical files and any activity data covering the final partial quarter of the study will be transmitted to the IHTC

Following subject withdrawal, the subject will be requested to meet with their local hemophilia physician to determine their ongoing treatment therapy/regimen.

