### 10.2 Institutional Review Board (IRB) Approval

A copy of the protocol, Investigator's Brochure, proposed Informed Consent Form and any other written subject information must be submitted to the IHTC IRB for written approval. A copy of the written IRB approval of the protocol and Informed Consent Form must be received by Genentech before recruitment of subjects into the study and shipment of investigational drug.

The Study Investigator must submit and, where necessary, obtain approval from the IRB for all subsequent protocol amendments and changes to the informed consent form. The Study Investigator should notify the IRB of deviations from the protocol or SAEs/reportable safety events at the site or reports of such events received from Genentech in accordance with local procedures.

The Study Investigator will be responsible for obtaining annual IRB approval and renewal throughout the duration of the study.

The Study Investigator will promptly report to the IRB all changes in research activity and all unanticipated problems involving risks to human subjects and will not make any changes in the research without prior approval from Genentech and the IRB, except where necessary to eliminate immediate hazards to human subjects.

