## 10.9 Data Monitoring

The IHTC is responsible for the oversight of subject safety.

Safety data collection will commence when each individual subject signs and dates the informed consent form and initiates study procedures and will continue until the study ends or the subject withdraws from the study, whichever occurs first. All SAEs will be reported to and reviewed by the Study Investigator. One non-study physician from the study site will review all SAEs, deaths or other unexpected events and report to the Study Investigator with recommendations. If a patient dies on study, the case will be evaluated in detail to determine its relatedness to the study drug and to determine if the study warrants stopping in the opinion of the Study Investigator.

Any drug-related SAE (SADR) will be reported through Genentech's reporting system, as will all AEs stipulated in **Section 6.11.3.2j**. The study site will maintain a record of all SAE reports, interpretations and recommendations which will be available for Genentech to review upon request. In addition, if a greater than expected number of breakthrough bleeding events, or the development of thrombosis or thrombotic microangiopathy (TMA) outside of the established associations occurs, treatment of the subject with Hemlibra (emicizumab) may be halted. If an anaphylactic reaction to Hemlibra (emicizumab) occurs, then treatment of that patient may be halted. The Study Investigator may withdraw a patient based upon their clinical discretion and patient safety.

During the course of the trial, the IHTC will review safety data at least at the following time points:

- On the occasion of every SAE, death or other unexpected event. The event will be assessed by a non-study physician from the IHTC who will report their findings to the Study Investigator. Any drug-related SAE (SADR) will also be reported through Genentech's reporting system
- Every 3 months on a subject-by-subject basis by a non-study physician from the IHTC
- Comprehensively by a non-study physician from the IHTC during every interim analysis (minimally at the 2-year midpoint of the study).

A non-study physician from the study site and the Study Investigator will make recommendations, if necessary, for study modification or termination because of concerns over

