### **10.10 Protocol Violations/Deviations**

Deviations from clinical protocol requirements will be reviewed and evaluated on an ongoing basis and, as necessary, appropriate corrective actions put into place.

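### The patient-level halting rule is mandatory in the synopsis but discretionary, and narrower in scope, in Section 10.9

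*Combined protocol and SAP*

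**What the plan says.** The halting rule for an individual patient is stated twice in the current protocol.

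- **Synopsis, Safety Analyses.** One sentence lists all four triggers. It begins "if a greater than expected number of breakthrough bleeding events, or the development of thrombosis, thrombotic microangiopathy (TMA" and closes with the consequence: "anaphylactic reaction to study medication occurs, the treatment of that patient will be halted". Neither thrombosis nor TMA carries a qualifier.
- **Section 10.9, Data Monitoring.** The rule is split over two sentences. The first covers excess bleeding, thrombosis and TMA, and ends "the development of thrombosis or thrombotic microangiopathy (TMA) outside of the established associations occurs, treatment of the subject with Hemlibra (emicizumab) may be halted". The second reads "If an anaphylactic reaction to Hemlibra (emicizumab) occurs, then treatment of that patient may be halted".

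Section 6.11.3.2i lists TMA, thromboembolic events and "Systemic hypersensitivity reactions and anaphylactic and anaphylactoid reactions" as Events of Special Interest, without the qualifier used in Section 10.9. On deviations, Section 10.2 states: "The Study Investigator should notify the IRB of deviations from the protocol or SAEs/reportable safety events at the site". Section 10.10 adds: "Deviations from clinical protocol requirements will be reviewed and evaluated on an ongoing basis". Section 7.6 gives a general power: "The Study Investigator has the right to involuntarily withdraw a subject from the study at any time for any reason".

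**The concern.** The same four events lead to a required stop in one place and an optional stop in the other. For TMA at least, Section 10.9 also narrows the event that counts, using a phrase found nowhere else in the protocol. A TMA judged to fall inside those associations may not trigger the Section 10.9 rule at all, whereas the synopsis requires a stop after any TMA.

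Two things are at stake. First, the investigator does not have a single instruction for the safety events that the protocol watches most closely. Second, whether continued dosing after such an event is a protocol deviation, to be notified to the IRB and reviewed for corrective action, depends on which section is applied.

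**Working it through.** No arithmetic is involved beyond counting, and the plan gives no figure to reproduce. The check sets the two texts side by side and then looks for anything that would reconcile them.

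**Step 1. Compare by trigger.**

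| Trigger | Synopsis | Section 10.9 | Obligation differs? | Scope differs? | Event of Special Interest (6.11.3.2i)? |
|---|---|---|---|---|---|
| Excess breakthrough bleeding | will | may | yes | no | no |
| Thrombosis | will | may, possibly with qualifier | yes | only if the qualifier covers both nouns | yes |
| TMA | will | may, with qualifier | yes | yes | yes |
| Anaphylaxis | will | may | yes | no | yes |

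Counts: the obligation differs for 4 of 4. Scope differs for 1 of 4 if the qualifier attaches to TMA alone, or 2 of 4 if it also covers thrombosis. Three of 4 fall under the Events of Special Interest.

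**Step 2. Compare by action once a trigger has occurred.** Stopping treatment is compatible with both texts for all four triggers (0 of 4 in conflict). Continuing treatment breaches the synopsis and complies with Section 10.9 for all four (4 of 4 in conflict).

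**Step 3. Is it one rule or two?** The two paragraphs run in parallel. Both cover the start of safety data collection, review of SAEs by a non-study physician and evaluation of any death, and both end with the same sentence on withdrawal at the investigator's discretion. Because that sentence is in both, it cannot explain the difference between *will* and *may*.

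**Step 4. Is one text superseded?** The change logs for Amendments 1 and 2 list neither Section 10.9 nor the halting rule. Both statements stand in version 3.0.

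**Step 5. Does anything else decide it?** There is no precedence clause between synopsis and body. Sections 5.3.2 and 7.3 continue weekly dosing until withdrawal or study termination and mention no safety halt. Sections 6.4 and 6.11.3.2i require monitoring and rapid communication of the special-interest events but give no halting instruction. Section 7.6 gives a right to withdraw a subject, not a duty. The written recommendations to Genentech under Section 10.9 concern modifying or terminating the study, not the patient-level rule. The synopsis states that there is no DSMB.

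**The case against.** The wording difference is hard to dispute. The case on the other side concerns its weight.

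- **The bleeding trigger has no threshold in either text**, so a breach of the synopsis cannot be demonstrated for that trigger and already rests on judgement. This stands: the 4 of 4 count is conditional on a trigger being accepted as met, and a breach that an outside observer could establish is limited to the other three.
- **A halt is not defined as temporary or permanent**, so a short hold followed by resumption might satisfy both texts. This is possible, but it adds an ambiguity and does not remove the conflict for a patient whose dosing is never interrupted.
- **The events reach oversight anyway.** Section 10.2 covers serious events as well as deviations, special-interest events go to Genentech within 15 days, and a non-study physician reviews every SAE and each subject every 3 months. These safeguards lower the practical risk. They do not say whether continued dosing was permitted.
- **The body is consistent with itself**, because only the synopsis contains a mandatory halt. That may indicate where the mismatch arose, but the other body sections are silent on halting, and silence does not establish which rule governs.
- **The Package Insert or Investigator's Brochure may define the qualifier.** That cannot be checked here. The supportable statement is that the protocol neither defines the phrase nor points to a source for it.
- **The study is small**, with about 10 subjects at one center under one Study Investigator. This limits how often the conflict can arise, but the instruction after such an event remains contradictory.

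**Conclusion.** The inconsistency is real and must be fixed. The current protocol gives two incompatible patient-level halting rules: the obligation differs for all four triggers, and the scope differs for TMA and possibly thrombosis. Three of the four triggers fall under the protocol's own Events of Special Interest, which justifies treating this as more than an editorial slip.

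The counts measure conflicting text; they are not an effect size, and no effect on the primary result is claimed. The conclusion assumes that both sections are operative in version 3.0, as the amendment logs indicate, and that no document outside the protocol sets the order of precedence. It does not depend on which reading of the qualifier is taken, because the obligation differs under either.

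**What to change.** Reconcile the synopsis (Safety Analyses) and Section 10.9 so that both state one rule, with the same force and the same events. Either define the associations mentioned in Section 10.9, by text or by reference to a named source, and say whether the phrase applies to TMA only or also to thrombosis, or remove it. Whether stopping is required or discretionary, and for which events, is a clinical choice for the sponsor; this review does not propose an answer.

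The cost is a protocol wording amendment, with no added patients, visits or procedures.

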### *Planned Interim Analyses*

Interim analyses will be conducted yearly at the discretion of the Study Investigator if sufficient patients are enrolled. At a minimum, an interim analysis will occur at the mid-point of the study (2-years following the date of informed consent of the first study subject).

## **Assessments with brief summary of methods & procedures**

### *Data Safety Monitoring Board (DSMB)*

No DSMB will exist for the study. One designated non-study physician from the IHTC will review all safety data and other unexpected events and report to the Study Investigator with recommendations.

*Pharmacokinetics*

No pharmacokinetic studies will be performed during the study

*Pharmacodynamics*

No pharmacodynamics studies will be performed during the study

*Quality of Life (QoL)*

The change in quality of life and activity with Hemlibra (emicizumab) prophylaxis will be evaluated during the study. QoL and activity will be assessed using Haem-A-QoL and EQ-5D-5L. Activity level may be assessed using a Fitbit or similar device to evaluate daily activity during the course of the study if such a device is standardly utilized by the subject, and the subject provides consent to export data from device.

*Biomarker Population*

No biomarker population analysis will be performed during the study

**Additional Details**

Due to the anticipated small study size, there will be no restrictions on BMI and the presence/absence of FVIII inhibitors.

## LIST OF ABBREVIATIONS AND DEFINITIONS OF TERMS

Ab	Antibody
Ag	Antigen
ACT	Activated clotting time
ADA	Anti-drug antibodies
ADR	Adverse drug reactions
AE	adverse event
AESI	Adverse event of special interest
ALT	Alanine aminotransferase
aPCC	Activated prothrombin complex concentrate
APC-R	Activated protein C resistance
aPTT	Activated partial thromboplastin time
AST	Aspartate aminotransferase
BMI	Body mass index
BU	Bethesda unit
CBC	Complete blood count
CD4	Cluster of differentiation 4 glycoprotein
CFR	Code of federal regulations
CHO	Chinese hamster ovary
CRF	Case report form
CRO	Contract research organisation
CT	Computed tomography
CTSP	Clinical trial safety portal
CTV	Adverse event case transmission verification
DOB	Date of birth
DSUR	Development safety update report
ELISA	Enzyme linked immunosorbent assay
EMA	European medicines agency
ePS	ePharmaSolutions
EQ-5D-5L	EuroQol Group questionnaire measuring health-related quality of life with 5 dimensions, and responses recording five levels of severity
EtMs	Events to monitor of medical and scientific concern
EU	European Union
EVCTM	Eudravigilance clinical trial module
FDA	Food and drug administration
FVIII	Factor VIII
FVIIIa	Factor VIII activated
FIX	Factor IX
FIXa	Factor IX activated
FX	Factor X

FXa	Factor X activated
GCP	Good clinical practice
Haem-A-QoL	Haemophilia quality of life questionnaire for adults
HAV	Hepatitis A virus
HBV	Hepatitis B virus
HCV	Hepatitis C virus
HEENT	Head, eyes, ears, nose, throat
HIPAA	Health information portability and accountability act
HIV	Human immunodeficiency virus
HRQoL	Health-related quality of life
IB	Investigator brochure
IHTC	Indiana Hemophilia and Thrombosis Center
IMP	Investigational medicinal product
IND	Investigational new drug
IRB	Institutional review board
ISTH	International Society on Thrombosis and Haemostasis
ITI	Immune tolerance induction
MRI	Magnetic resonance imaging
NBU	Nijmegen bethesda unit
PD	Pharmacodynamics
pdFVIII	Plasma-derived factor VIII
PI	Package insert
PK	Pharmacokinetics
PRBC	Packed red blood cells
PRO	Patient reported outcome
PT	Prothrombin time
PT	Preferred term
QoL	Quality of life
rFVIIa	Factor VII activated
rFVIII	Recombinant factor VIII
SADR	Serious adverse drug reaction
SAE	Serious adverse event
SD	Standard deviation
SOC	System organ class
TMA	Thrombotic microangiopathy
TT	Thrombin time
U	Unit
ULN	Upper limit of normal
US	United States
VWF	Von Willebrand factor
VWF:Ag	Von Willebrand factor antigen

This page is left blank

## 1 INTRODUCTION

### 1.1 Background Information on the Product

Hemlibra (also known as emicizumab, ACE910 and RO5534262) is a humanized monoclonal modified immunoglobulin G4 (IgG4) antibody with a bispecific antibody structure produced by recombinant DNA technology in Chinese hamster ovary (CHO) cells. Hemlibra (emicizumab) bridges activated factor IX (FIXa) and factor X (FX) to restore the function of missing activated factor VIII (FVIIIa) that is needed for effective hemostasis.

In patients with hemophilia A, hemostasis can be restored irrespective of the presence of factor VIII (FVIII) inhibitors, as emicizumab shares no sequence homology with FVIII. Due to its pharmacokinetic (PK) properties, emicizumab can be administered subcutaneously at a frequency that is less than that of other currently available therapies for hemophilia A. Therefore, this novel compound may have the potential to significantly change the treatment of patients with hemophilia A, with or without FVIII inhibitors, who are in need of prophylactic treatment to prevent bleeding episodes.

Hemlibra (emicizumab) is currently indicated for prophylactic use in the US and other countries in patients with hemophilia A and FVIII inhibitors to prevent or reduce the incidence of bleeding events.

### 1.2 Hemophilia

Hemophilia A is an X-linked recessive bleeding disorder characterized by congenital underproduction of or dysfunction of FVIII, an essential protein in promoting clot formation. Hemophilia A accounts for approximately 80% of all cases of hemophilia. The incidence of hemophilia A is approximately 1 in 5,000 live-born male births or 1 out of every 10,000 live births [Franchini and Mannucci 2013, Centers for Disease Control and Prevention 2014, National Institutes of Health 2014]. No racial differences have been reported in the distribution of patients with hemophilia. The number of patients with hemophilia A registered in 2015 in various regions across the world, include 4,986 individuals in Japan (3.9/100,000 people), 17,285 in North America (4.8/100,000 people; [Canada estimate from 2014]), and 21,410 in the five major European nations (United Kingdom, France, Germany, Italy, and Spain; 6.7/100,000 people; [Spain estimate from 2011 and Italy estimate from 2014]) [World Federation of Hemophilia 2012, World Federation of Hemophilia 2013, World Federation of Hemophilia 2016].

The main bleeding sites are intra-articular, intramuscular, subcutaneous, intraoral, intracranial, gastrointestinal, and intranasal. In particular, repeated intra-articular bleeds are a major contributor to decreased HRQoL in patients with hemophilia A, as the joint damage associated with multiple hemarthrosis may progress to hemophilic arthropathy [Gringeri, Leissinger et al. 2013]. In advanced forms, hemophilic arthropathy is associated with significant joint pain, swelling, and limited range of motion, which may ultimately require surgical intervention, including joint replacement. Although less frequently than musculoskeletal bleeds, patients with

hemophilia A can also develop intracranial or severe gastrointestinal bleeding resulting in death [World Federation of Hemophilia 2012].

The severity of (and bleeding risk associated with) hemophilia A is classified in accordance with endogenous FVIII activity in the plasma. Those with FVIII activity less than 1% have severe disease; between 1% and 5%, moderate disease; and between 5% and 50%, mild disease. Patients with severe hemophilia A can suffer several spontaneous bleeding episodes each month – much more frequently than those with moderate or mild disease. In addition, such patients are at a greater risk for having life-threatening bleeds. Hence, the maintenance of FVIII activity levels about 1-3% with FVIII prophylaxis is desired, in order to effectively reduce bleeding episodes, morbidity (eg, arthropathy), mortality, as well as to improve HRQoL in patients with severe hemophilia A [Srivastava, Brewer et al. 2013].

### **1.3 Hemophilic Pseudotumor**

Hemophilic pseudotumor is a rare complication of hemophilia that occurs in 1-2% of patients with severe hemophilia [van Ommeren, Mooren et al. 2000]. It is observed more frequently in geographic areas where hemophilia is diagnosed late, treatment is inconsistently available, prophylaxis is not used due to resource constraints, and in patients who do not recognize that a bleeding event has occurred (eg, moderate or mild deficient patients who experience infrequent bleeds/injuries). Pseudotumors are more commonly observed in adults than pediatric patients [Magallon, Monteagudo et al. 1994] They may be present in patients with hemophilia either with or without an inhibitor and are more common in patients with inhibitors where hemostasis is less well controlled.

A hemophilic pseudotumor consists of an encapsulated progressive cystic swelling of muscle and/or bone caused by recurrent hemorrhage which can cause a serious complication to both life and limb. Pseudotumors have been reported in a wide variety of bones and soft tissues [Liu, White et al. 1988] where repeated and unresolved hematomas lead to encapsulation, calcification and progressive enlargement, with subsequent erosion of adjacent bone. Most commonly the pseudotumor occurs in the pelvis and long bones of lower extremity; they are also observed in muscles, particularly the iliacus, vastus lateralis and soleus. Pseudotumors are best treated early; if left untreated they can result in compression pressure necrosis of adjacent structures, further bleeding, infection, erosion and loss of function and/or life. Complicating early diagnosis is the fact that patients with pseudotumors may be asymptomatic or stable for long periods of time (sometimes decades) before developing complications [Ahlberg 1975, Magallon, Monteagudo et al. 1994, van Ommeren, Mooren et al. 2000].

Hemophilic pseudotumors are most readily diagnosed and monitored using CT or MRI.

